STUDY DESIGN	
This is a Phase 3, multi-center, randomized, double-blind, placebo-controlled, study to assess the efficacy and safety of SD-101-6.0 cream vs. placebo (SD-101-0.0) on lesions in patients with Simplex, Recessive Dystrophic, or Junctional non-Herlitz Epidermolysis Bullosa.
 
SD-101-6.0 cream or placebo (SD-101-0.0) will be applied topically, once a day to the entire body for a period of 90 days. Patients will be randomized on a 1:1 basis. Patients will have 1 target wound selected at baseline by the Investigator. Selected target wound must be at least 21 days old (size 10 to 50 cm²). Photographic confirmation of the target wound location will be collected at baseline, and the picture saved from the first visit will be used to confirm location of the target wound at subsequent visits.
 
The patient will return to the study site for Visit 2 (14 days ±5 days from baseline), Visit 3 (30 days ±7 days from baseline), Visit 4 (60 days ±7 days from baseline), and Visit 5 (90 days ±7 days from baseline) to have the

target wound, previously identified at baseline, re-assessed for the level of healing. In addition, itching, pain, body surface area index (BSAI), and scarring of healed target wound will also be assessed at each visit. The ARANZ SilhouetteStar™ will be used to measure the target wound at all visits.

STUDY OBJECTIVE

The primary objective is to compare the efficacy and safety of SD-101-6.0 vs. SD-101-0.0 (placebo) in patients with Simplex, Recessive Dystrophic, or Junctional non-Herlitz Epidermolysis Bullosa.

STUDY EFFICACY ENDPOINTS

Primary Efficacy Endpoints

The primary efficacy endpoints for this study are:

- Time to complete target wound closure within 3 months
- The proportion of patients experiencing complete closure of their target wound within 3 months

Key Secondary Efficacy Endpoints

The key secondary measures of efficacy include:

- Proportion of patients experiencing complete closure of their target wound within 2 months
- Proportion of patients experiencing complete closure of their target wound within 1 month
- Change in lesional skin based on BSAI at Month 3, compared to Baseline
- Change in Total Body Wound Burden based on BSAI at Month 3, compared to Baseline
- Change in itching assessed at Day 7, compared to Baseline
- Change in pain assessed at Day 7, compared to Baseline

Other Secondary Efficacy Endpoints

- Change in Total Body Wound Burden based on BSAI at Week 2 and Months 1 and 2, compared to Baseline
- Percent change from Baseline in Total Body Wound Burden based on BSAI at Week 2 and Months 1, 2, and 3
- Change in lesional skin based on BSAI at Week 2 and Months 1 and 2, compared to Baseline
- Percent change in lesional skin based on BSAI at Week 2 and Months 1, 2, and 3, compared to Baseline

- Presence of scarring of healed target wound at the visit where the complete closure is documented
- Change in target wound characteristics (ie, inflammation, blistering, granulation tissue, erythema, exudate) at Week 2 and Months 1, 2, and 3, compared to Baseline
- Change in itching and pain at Days 1 to 6, Week 2, Months 1, 2, and 3, compared to Baseline
- Proportion of patients experiencing target wound closure within Week 2

PLANNED SAMPLE SIZE Approximately 150 patients will be enrolled.

- PATIENT POPULATION Inclusion Criteria**
1. Informed Consent form signed by the patient or patient's legal representative; if the patient is under the age of 18 but capable of providing assent, signed assent from the patient.
 2. Patient (or caretaker) must be willing to comply with all protocol requirements.
 3. Diagnosis of Simplex, Recessive Dystrophic, or Junctional non-Herlitz EB.
 4. Patient must have 1 target wound (size 10 to 50 cm²).
 5. Patients 1 month and older.
 6. Target wound must be present for 21 days or more.

- PATIENT POPULATION Exclusion Criteria**
1. Patients who do not meet the entry criteria outlined above.
 2. Selected target wound cannot have clinical evidence of local infection.
 3. Use of any investigational drug within the 30 days before enrollment.
 4. Use of immunotherapy or cytotoxic chemotherapy within the 60 days before enrollment.
 5. Use of systemic or topical steroidal therapy within the 30 days before enrollment. (Inhaled steroids and ophthalmic drops containing steroids are allowed)
 6. Use of systemic antibiotics within the 7 days before enrollment.
 7. Current or former malignancy.
 8. Arterial or venous disorder resulting in ulcerated lesions.
 9. Pregnancy or breastfeeding during the study. (A urine pregnancy test will be performed at screening and every 30 days until the final visit for female patients of childbearing potential)

10. Females of childbearing potential who are not abstinent and not practicing a medically acceptable method of contraception.

FORMULATION/DOSE	SD-101 cream will be applied topically, once a day to the entire body for a period of 90 days. Application will consist of blinded SD-101-6.0 or SD-101-0.0 (placebo).
ROUTE OF ADMINISTRATION	Topical administration of SD-101-6.0 dermal cream or SD-101-0.0 (placebo).
DURATION/FREQUENCY OF TREATMENT	Topical application of SD-101 once daily over the entire body surface for 90 days.
SAFETY ASSESSMENTS	The safety of SD-101-0.0 and SD-101-6.0 will be assessed by monitoring tolerability, adverse events (AEs), and physical examinations.
STATISTICAL METHODS	
Primary Efficacy Parameters: The primary efficacy endpoints for this study are time to complete target wound closure within 3 months and the proportion of patients experiencing complete closure of their target wound within 3 months. These variables will be compared between SD-101-6.0 and SD-101-0.0 (placebo), and tested via a step-down procedure beginning with the time to complete target wound closure.
 
Time to event analyses will be performed using a Kaplan-Meier approach, where the event is target wound closure measured from the date of randomization (study day 0) to the date of wound closure. The two treatment groups will be compared with respect to the two primary endpoints using Cox Proportional Hazards model and Logistic Regression, respectively. Covariates will be included in the Cox Proportional Hazards and Logistic Regression models. The approach to evaluating these and secondary variables will be summarized in a fully detailed Statistical Analysis Plan.
 
Assumptions underlying the sample size estimation are that 35% of placebo patients will experience complete closure of their target wound at or before the 3-month follow-up visit and at least 60% of patients treated with SD-101-6.0 will experience complete closure of their target wound by this time (hazard ratio approximately 2.127, assuming exponential hazards over time). Using

these assumptions and a 1-sided overall alpha of 0.025, approximately 150 patients will be required (75 in each group) to provide approximately 86% power for time to complete target wound closure. There is estimated 85% power for proportion of patients with complete target wound closure.

Safety Parameters:

Adverse events will be coded using MedDRA. The number of events, incidence, and percentage of treatment-emergent AEs (TEAE) will be calculated overall, by system organ class (SOC), and by preferred term. Treatment-emergent AEs will be further summarized by severity and relationship to investigational product. Adverse events related to investigational product, AEs leading to withdrawal, serious AEs (SAEs), and deaths will be summarized/listed.

Baseline and Month 3 physical examination results, together with changes during the study period, will be described using summary statistics.

3. LIST OF ABBREVIATIONS

ADR	Adverse Drug Reaction
AE	Adverse Event
BSA	Body Surface Area
BSAI	Body Surface Area Index
CRF	Case Report Form
DMC	Data Monitoring Committee
EB	Epidermolysis Bullosa
EBS	Epidermolysis Bullosa Simplex
ET	Early Termination
FDA	Food and Drug Administration
FLACC	Face, Legs, Activity, Cry, Consolability
GCP	Good Clinical Practice
ICH	International Conference on Harmonization
IEC	Independent Ethics Committee
IRB	Institutional Review Board
ISC	Independent Statistical Center
ITT	Intent-to-treat
IWRS	Interactive Web Response Services
MEDRA	Medical Dictionary for Regulatory Activities
PP	Per Protocol
RDEB	Recessive Dystrophic Epidermolysis Bullosa
SAE	Serious Adverse Event
SD-101-0.0	SD-101 cream containing 0% allantoin (placebo)
SD-101-1.5	SD-101 cream containing 1.5% allantoin
SD-101-3.0	SD-101 cream containing 3% allantoin
SD-101-6.0	SD-101 cream containing 6% allantoin
SD-101-9.0	SD-101 cream containing 9% allantoin
TEAE	Treatment Emergent Adverse Event
U.S.	United States
WMA	World Medical Association

5. BACKGROUND INFORMATION

Epidermolysis Bullosa (EB) is a rare group of inherited disorders that typically manifest at birth as blistering and lesion formation on the skin and, in some cases, the epithelial lining of other organs, in response to little or no apparent trauma. In consequence, the skin is extremely fragile which can result in shearing of the skin, causing a high risk of infection. All forms of EB are both debilitating and life threatening. In some EB subtypes, high mortality occurs before the age of 1 (Junctional Herlitz), and others in adolescences to early adulthood, typically due to infection or failure to thrive. In addition, children surviving into their 20's and 30's are also at risk for development of a virulent form of squamous cell carcinoma, which is in many cases fatal.

There are no standard of care products available to treat the dermal manifestations of EB, and there is no approved drug for EB in either Europe or the United States. There have been numerous studies published on potential treatments for skin manifestations associated with EB, including vitamin E therapy, systemic phenytoin, topical nonsteroidal agents, cyproheptadine, tetracycline, and dapsone. No controlled studies showed clinical benefit of any therapy. Newer exploratory treatments including skin grafts, bioengineered skin products, and gene therapy have been unsuccessful to date.

5.1. Overview of Active Ingredient and Drug Product (SD-101)

Pharmacology of Allantoin

The precise mechanism of action of allantoin in wound healing has not yet been defined. There are many animal wound and EB models, however, no product to date effective in any of these models has demonstrated effectiveness in humans. SD-101 was tested in the current appropriate wound model in EB, which is EB patients, and is the first product that has produced beneficial effects in healing of lesional skin, and appears to reduce the outbreaks of blistering. Data from the literature suggest that allantoin does not work via a single activity, but rather appears to affect multiple aspects of the processes involved in wound healing. These include reduction of inflammation, induction of growth of healthy tissue, stimulation of collagen as well as stimulation of granulation in ulcers, including tissue differentiation and epithelialization. In addition, allantoin has demonstrated bacteriostatic and bactericidal effects, and appears to aid in removing necrotic tissue.

Pharmacokinetics of Allantoin

Allantoin is a compound that is found endogenously in rats, rabbits, pigs, dogs, monkeys, in addition to a lower extent in humans. Allantoin is the main end product of purine metabolism in most mammals, and is produced from metabolism of uric acid via the enzyme, uricase. In rats and other mammals, uricase is present within peroxisomes of liver parenchymal cells. In man and great apes, uricase is not present, so that the primary end product of purine metabolism is uric acid. However, small amounts of allantoin are produced in great apes and humans via non-enzymatic conversion of uric acid.

SD-101 Topical Cream

Allantoin is the active ingredient contained within SD-101 skin cream, which is a commercially viable formulation with demonstrated stability of allantoin for several years at concentrations up to 9%. The capability to deliver the active moiety to the target in skin is key in topical products, since the skin is an effective barrier to penetration. In a series of flux studies with SD-101 containing allantoin ranging from 0.5 to 9%, penetration across the various skin barriers was dose-related.

SD-101 has been developed to overcome the inherent limited solubility and stability of allantoin, allowing the ability to formulate allantoin at higher concentrations. In consequence, allantoin concentrations as high as 9% can be achieved in a topical product whereas the amount in existing cosmetics as an inactive excipient is typically less than 0.2%.

SD-101 cream is currently being developed as a new topical therapy for the treatment of lesional skin in patients with EB. The same product is foreseen for adult and pediatric patients.

5.2. Summary of Animal and Human Studies with SD-101

Toxicology studies assessing topical administration of SD-101-9.0 in multiple species demonstrated the lack of local or systemic effects with this active in the current formulation. The lack of systemic effects with allantoin in animals administered SD-101 topically was further supported by additional safety information obtained with intravenous administration of allantoin in the monkey. Peak intravenous blood levels in the monkeys were achieved that were approximately 700 times higher than endogenous levels measured in published healthy human subject pharmacokinetic studies, without any demonstrated clinical chemistry abnormalities or organ toxicity at either the macroscopic or microscopic level. Additional toxicology studies with SD-101-9.0 demonstrated that this product was non-sensitizing in the guinea pig and did not produce ocular irritation in the rabbit. Lastly, from examination of the excipients and the active ingredient, allantoin, for the ability to absorb light in the UV-A and / or UV-B ranges, there were no demonstrated concerns of potential phototoxicity with use of this product.

Studies in normal volunteers with topical use of SD-101 (SD-101-0.0, SD-101-3.0, SD-101-6.0, and SD-101-9.0), and in EB Patients with topical usage of SD-101 (SD-101-1.5, and SD-101-3.0) demonstrate to date that allantoin at these concentrations (in this formulation) has not produced any local or systemic adverse effects of concern. In addition, topical administration of SD-101 (SD-101-1.5) was found to be non-sensitizing in healthy subjects.

An open-label study using SD-101-3.0 was previously conducted. Eight EB patients with a diagnosis of EB (Simplex, Recessive Dystrophic, or Junctional) based on diagnostic immunomapping or electron microscopy, were treated with SD-101-3.0 cream once applied daily to their entire skin surface, for a period up to 3 months. Application of the

cream was non-irritating and did not produce any discomfort when applied to either unblistered areas or open lesions. The patients treated with SD-101-3.0 for three months showed significant improvements in the complete healing of lesions (typified by the results with the target wounds), clinically meaningful reductions in the extent of total skin surface involvement with active disease (body surface area [BSA]), and reduced pain and itching. Daily use of SD-101-3.0 cream in treatment up to 3 months was well tolerated by all patients in the study, with no related adverse events (AEs) noted. There were no serious AEs (SAEs) that occurred in any patient during the 3 month treatment period. In addition, there was good compliance on usage of the product on the entire skin surface, based on the soothing and non-irritating effects of the SD-101 creams.

A Phase 2B study (SD-003) was completed with two strengths of SD-101 (containing 3% and 6% allantoin: identified as SD-101-3.0 and SD-101-6.0) with a matching vehicle control (SD-101-0.0). The primary endpoint of this study was the complete closure of the patient's target chronic wound within one month. Secondary endpoints comprised effects on improvement in body coverage in lesional skin (including blistering), pain, and itching. In addition, patients from study SD-003 were offered to roll-over into an open-label extension study (Study SD-004) to continue treatment with SD-101-6.0 to collect long term safety data as well. The results of Study SD-003 support that SD-101-6.0 is the most efficacious concentration and provided good safety and will be the concentration used in this registration study (SD-005), and compared against the placebo group receiving SD-101-0.0.

The design of studies SD-003 (Phase 2B) and SD-005 (Phase 3) are essentially identical, with differences in number of treatment arms and sample size, and minor modification of the minimum target wound size at study entry. Patients completing SD-005 will also be offered a roll-over option (Study SD-006) to receive SD-101-6.0.

6. RATIONALE FOR STUDY

SD-005 is a Phase 3 study to evaluate the efficacy and safety of SD-101-6.0 relative to a placebo cream in the treatment of EB patients. This confirmatory study follows the demonstration in a Phase 2B study that SD-101-6.0 stimulated wound closure and had an acceptable safety profile.

The aim is to assess the safety and efficacy of SD-101-6.0 cream vs. placebo in the treatment of patients with Epidermolysis Bullosa.

7. STUDY OBJECTIVE AND PURPOSE

7.1. Objective

The primary objective is to compare the efficacy and safety of SD-101-6.0 vs. SD-101-0.0 (placebo) in patients with Simplex, Recessive Dystrophic, or Junctional non-Herlitz Epidermolysis Bullosa.

8. SELECTION AND WITHDRAWAL OF PATIENTS

8.1. Patient Numbers

Approximately 150 patients will be enrolled at study sites worldwide.

8.2. Inclusion Criteria

Patients must meet all of the following inclusion criteria to be eligible for enrollment into the study.

1. Informed Consent form signed by the patient or patient's legal representative; also, if the patient is under the age of 18 but capable of providing assent, signed assent from the patient.
2. Patient (or caretaker) must be willing to comply with all protocol requirements.
3. Diagnosis of Simplex, Recessive Dystrophic, or Junctional non-Herlitz EB.
4. Patient must have 1 target wound (size 10 to 50 cm²).
5. Patients 1 month and older.
6. Target wound must be present for 21 days or more.

8.3. Exclusion Criteria

Patients with any of the following exclusion criteria will not be eligible for enrollment into the study.

1. Patients who do not meet the entry criteria outlined above.
2. Selected target wound cannot have clinical evidence of local infection.
3. Use of any investigational drug within the 30 days before enrollment.
4. Use of immunotherapy or cytotoxic chemotherapy within the 60 days before enrollment.
5. Use of systemic or topical steroidal therapy within the 30 days before enrollment. (Inhaled steroids and ophthalmic drops containing steroids are allowed)
6. Use of systemic antibiotics within the 7 days before enrollment.
7. Current or former malignancy.
8. Arterial or venous disorder resulting in ulcerated lesions.
9. Pregnancy or breastfeeding during the study. (A urine pregnancy test will be performed at screening and every 30 days until the final visit for female patients of childbearing potential)
10. Females of childbearing potential who are not abstinent and not practicing a medically acceptable method of contraception.

8.4. Withdrawal Criteria/Study Discontinuation

Patients may withdraw from the study at any time without stating a reason and without prejudice to further treatment. The Investigator may withdraw a patient from the study and discontinue study treatment and assessments at any time due to safety concerns or concerns about the patient's compliance with study requirements and procedures. Full skin examination will be performed at each visit. If SD-101 causes any significant rash that has not occurred previously in the patient, the Investigator should consider discontinuing the patient. In addition, if lesions appear to significantly worsen above the normal cycle seen in the patient, with use of SD-101, the Investigator should consider discontinuing the patient. If a patient discontinues treatment at any time after entering the study, the Investigator will make every effort to ensure the patient returns for all study visits.

Early discontinuation of any patient who has given informed consent/assent to participate will be recorded including the reason for discontinuation. The primary reason for a patient withdrawing prematurely will be selected from the following standard categories of early discontinuations.

1. Adverse Event (Adverse Reaction): Clinical events occurred or laboratory results are reported that in the medical judgment of the Investigator are grounds for discontinuation in the best interests of the patient.
2. Withdrawal of Consent: The patient desired to withdraw from further participation in the study. The patient is not obligated to provide any reason for withdrawal of consent, but where a reason is given this will be recorded on the eCRF.
3. Protocol Violation: The patient failed to adhere to the protocol requirements, at the Investigator's discretion.
4. Lost to Follow-Up: The patient stopped coming for visits and study personnel were unable to contact the patient.
5. Other: The patient was terminated for a reason other than those listed above, such as, termination of study by Sponsor or enrolled in the study by error when they did not meet inclusion/exclusion criteria.

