8.5. Handling of Withdrawals

Although a patient is not obligated to give his/her reason for withdrawing prematurely, the Investigator will make a reasonable effort to obtain the reason while fully respecting the patient's rights. Every effort will be made to ensure the patient returns for all study visits, as a safety measure. If there is a medical reason for withdrawal, the patient will remain under the supervision of the study physician until in satisfactory health. In the case of withdrawal due to an AE the patient will be followed as per [Section 11.3](#). Reasonable efforts will be made to contact a patient who fails to attend any follow-up appointments, in order to ensure that he/she is in satisfactory health.

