10.7.1. Prohibited Medications

The use of immunosuppressive agents or corticosteroids (oral, rectal, intravenous, and topical) are prohibited (however, limited steroid use is acceptable for planned medical procedures, including but not limited to, esophageal dilatation). Use of prohibited medications during the trial may result in the withdrawal of the subject based on the assessment by the Investigator and medical monitor.

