13. END OF THE STUDY

The end of the study will be defined as the last patient's last visit.

The study will be terminated early if, in the opinion of the Sponsor, Investigators, or IRBs, an unacceptable risk to the safety and welfare of patients is posed by the continuation of the study in light of review of the key unexpected AEs occurring during the trial.

Within the provisions of informed consent / assent and good clinical judgment with respect to safety, every attempt will be made to have patients complete the study.

The following reasons are grounds to terminate a patient's participation in the study:

1. Patient develops intolerable adverse effects, including but not limited to:
 - Severe and widespread dermatological reactions beyond the area of application.
 - Severe local reactions requiring systemic steroid therapy.
2. Any patient who becomes significantly noncompliant with study drug administration, study procedures, or study requirements should be withdrawn from study treatment when the circumstances increase risk to the subject or substantially compromise the interpretation of study results.
3. The patient's health would be jeopardized by continued participation.
4. Investigator judgment deems it appropriate.
5. The patient wishes to withdraw for any reason.
6. The Sponsor elects to end the study, or any portion thereof, for any reason.

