## **7.3. Handling of Dropouts or Missing Data**

For the time to wound closure endpoint, data will be right censored at 3 months or at the time of patient's withdrawal from the study. For the second primary endpoint and for the binary secondary endpoints of wound closure, the first method of imputation for missing data will be Multiple Imputation (MI) using the Missing At Random (MAR) assumption. As clarified in the NTF, if the target wound closure occurred at a prior visit, the target wound is considered closed at all subsequent visits that took place. In such a case, no imputation is required for subsequent visits.

For the first MAR based multiple imputation, the MI procedure of the SAS® system will be used to generate sets of data with missing values imputed from observed data. It is expected that the pattern of missing data will be monotonic, with slight deviations being corrected by the Markov Chain Monte Carlo (MCMC) method of the MI procedure.

As per clarification in the NTF, after the MCMC correction, the rounding will be performed for the binary endpoint. If imputed values are greater than or equal to 0.5, the value is set to 1 and anything else is set to 0.

Linear regression will be employed to model the missing continuous data and a logistic regression model will be used for the binary data, with the following covariates included in the imputation model: treatment, EB type, Baseline characteristics of a given endpoint (as described in Section 7.2), and non-missing data from earlier time points. As per clarification in the NTF, if the Week 2 data for wound closure are missing, there are no previous visit data available to utilize in the imputation procedure. Therefore, patients with missing Week 2 wound closure data will be excluded from analysis. The imputed datasets will be analyzed using the methodology

described in Section 8. The results from the analysis of the multiple imputed datasets will be combined by the MIANALYZE procedure of the SAS system. The seed number to be used will be 010005 and the number of imputations is planned to be 5.

The final p-value, estimate of regression coefficient for treatment effect, and the 95% CI of the estimate of the treatment effect on each multiply-imputed dataset will be generated from the MIANALYZE procedure of SAS.

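### Protocol wording leaves it to the site whether target-wound visits stop when a patient is withdrawn for non-compliance; where they stop, the deciding Cox analysis censors the patient and moves away from the ITT effect

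*Protocol*

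**What the plan says.** **Assessments may end.** Protocol 8.4 allows the investigator to "withdraw a patient from the study and discontinue study treatment and assessments at any time due to safety concerns or concerns about the patient's compliance". Section 13 opens its list with "The following reasons are grounds to terminate a patient's participation in the study" and includes significant non-compliance.

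**Visits continue, or only treatment ends.** On the remaining visits, the same paragraph of 8.4 closes with "If a patient discontinues treatment at any time after entering the study, the Investigator will make every effort to ensure the patient returns for all" of them. Section 8.5, which excepts no reason for withdrawal, says "Every effort will be made to ensure the patient returns for all study visits, as a safety measure". The non-compliance item in Section 13 says that such a patient "should be withdrawn from study treatment when the circumstances increase risk to the subject or substantially compromise the interpretation of study results".

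**Unspecified.** Protocol 10.7.1 says "Use of prohibited medications during the trial may result in the withdrawal of the subject based on the assessment by the Investigator and medical monitor". It does not say whether the withdrawal is from treatment or from the study, and it does not mention visits.

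**Analysis.** For time to closure, SAP 7.3 states that "data will be right censored at 3 months or at the time of patient's withdrawal from the study". Protocol 12.1 and 12.4 and SAP 8.6.1.1 agree. SAP 6.3.1 and 7.5 make this endpoint, analysed in all randomized patients, the sole test of study success.

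**The concern.** Whether a non-compliant patient has a 90-day outcome or a censored one depends on which sentence the site follows. That choice is made after randomization and can depend on treatment, because cream that seems not to work may be applied less faithfully. An ITT hazard ratio should compare the arms as randomized, including time after a patient stops applying the cream. If that time is cut off, the estimate drifts toward a comparison of those who kept complying.

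No planned analysis would show this on the deciding endpoint. In SAP Table 3 every Cox and log-rank analysis of time to closure, ITT and PP, uses censoring. The PP population also excludes patients below 70% diary compliance. The MNAR and missing-as-failure analyses (SAP 7.3, 8.6.1.2) apply only to the second primary endpoint.

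**Working it through.** **1. The plan's own power figure (Protocol 12.1).** Inputs: 35% and 60% closure by 3 months, 75 per arm, one-sided alpha 0.025, exponential hazards.
- HR = ln(0.40)/ln(0.65) = 2.127.
- Expected events = 75 × 0.35 + 75 × 0.60 = 71.25.
- Freedman power = Φ(√71.25 × (2.127 − 1)/(2.127 + 1) − 1.96) = Φ(3.042 − 1.960) = 86.0%.

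The stated 86% is reproduced. It has no allowance for withdrawal, since the number required and the number enrolled are both 150.

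**2. Withdrawal unrelated to prognosis.** Simulation with 400,000 patients per arm, visits at Days 14, 30, 60 and 90, and Cox with treatment only. Three assumptions are not in the documents: the share withdrawn (equal in both arms), a withdrawal time uniform over Days 1–60, and an active-arm hazard that returns to the placebo hazard on stopping. Events and Freedman power are scaled to 75 per arm.

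| Withdrawn per arm | HR, visits kept | HR, censored | Log-HR shift | Events, kept / censored | Power, kept / censored |
|---|---|---|---|---|---|
| 5% | 2.08 | 2.12 | 0.02 | 70.6 / 68.6 | 84% / 85% |
| 10% | 2.05 | 2.13 | 0.04 | 70.1 / 66.1 | 82% / 84% |
| 20% | 1.96 | 2.12 | 0.08 | 69.0 / 60.9 | 77% / 80% |

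The shift is ln(HR censored / HR kept); for example ln(2.13/2.05) = 0.04 and ln(2.12/1.96) = 0.08. Against a standard deviation of log HR of about 0.25 (trial-size simulations), these are 0.04/0.25 = 16% and 0.08/0.25 = 32%. A separate run at 75 per arm, with stopping between Days 10 and 45, gave 2.11 against 2.13 at 2% withdrawn, a shift of 0.01.

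**3. Withdrawal related to prognosis.** Assume 25% poor healers at a quarter of the hazard, in the same mix in both arms. In an arm with departures, half the poor healers and 5% of the others leave (0.25 × 0.50 + 0.75 × 0.05 = 16% of that arm). Stopped active patients again revert to the placebo hazard.

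| Who leaves | HR, visits kept | HR, censored | HR, observed compliers |
|---|---|---|---|
| Both arms alike | 1.98 | 2.08 | 2.08 |
| Active only | 1.97 | 2.23 | 2.29 |
| Placebo only | 2.05 | 1.90 | 1.86 |

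Each time the estimate moves toward the observed-complier contrast, upward in the first two rows and downward in the third. In the second row it passes the full-compliance value of 2.05.

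**4. Type I error.** With both arms at 35% closure, one-sided rejection was 2.6% with visits kept and 2.7% with censoring (20% withdrawn per arm), and 2.5% against 2.7% (5% placebo, 15% active). The nominal level is 2.5%. This covers the mechanism of step 2 only, not one-sided loss of poor healers.

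**5. A closure seen after recorded withdrawal.** Take a patient recorded as withdrawn on Day 40 who attends on Day 60 with a closed wound (illustrative days). SAP 7.3 read literally censors at Day 40. SAP 6.2.2 uses the first closure whatever the visit window and says that all available data are used, which suggests an event at Day 60. Under SAP 8.6.1.1 the patient is a responder for the second primary endpoint. The plan does not say which reading governs the first.

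**The case against.** The best defence is that retention is the protocol's default. The last sentence of that 8.4 paragraph, Section 8.5 and Section 13's aim that patients complete the study all favour continued visits; stopping assessments is only an option. That stands, and the number affected may be small. It does not remove the option, and nothing says which sentence prevails when a site uses it.

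Non-compliance is also not the same as withdrawal. Diary compliance below 70% removes a patient from PP (Protocol 12.2), not from ITT. That stands too: the percentages above are assumed shares withdrawn, not shares non-compliant.

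A reader might infer four stronger points that the documents do not support:
- **That 10.7.1 contradicts the other sections.** It is silent on visits, so it is ambiguous.
- **That censoring always flatters the cream.** The placebo-only case goes the other way.
- **That closures after withdrawal are definitely discarded, so that the two primary endpoints are bound to disagree.** SAP 6.2.2 leaves this open.
- **That the false-positive rate is at risk.** Under the reversion mechanism it is essentially unchanged, because if the cream does nothing, stopping it changes nothing.

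**Conclusion.** The conflict over follow-up of non-compliant patients is real and feeds the analysis that decides success. Its effect is a change in what the hazard ratio estimates, plus lost events; the 86% power calculation is not in error.

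If stopped active patients revert to placebo healing, the shift is upward: 0.04–0.08 in log HR at 10–20% withdrawn per arm, with about 4 to 8 events lost (70.1 − 66.1 = 4.0; 69.0 − 60.9 = 8.1), and 0.01–0.02 at 2–5%. If who leaves depends on prognosis, the shift can go either way. All these sizes rest on assumed withdrawal shares, because the documents give none. The effect is near zero if few patients are withdrawn. Whether a closure after recorded withdrawal counts in the first primary endpoint is a separate ambiguity in the SAP.

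**What to change.** - **Protocol 8.4, 8.5, 10.7.1 and 13.** Reconcile them so that, whatever is decided clinically about treatment, non-compliance or prohibited-medication use does not by itself end the scheduled target-wound assessments unless consent is withdrawn. State in 10.7.1 what the withdrawal is from. This takes no position on when treatment should stop.
- **SAP 7.3 and 8.6.1.1.** State that a closure seen at any attended visit through Month 3, including after treatment stops, is an event in the Cox analysis, and that a patient without closure is censored at the last wound assessment.

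The cost is a protocol wording change, a short SAP statement, a few already scheduled visits, and possibly a slightly less favourable hazard ratio. SAP Amendment 1 postdates database lock, so protocol wording cannot recover visits already missed. The SAP rule can still be clarified, and if that is done after lock the Cox result should be shown under both readings.
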